16.2 DERIVED VARIABLES

During the open-label treatment period, participants will record via the eDiary their daily IBS-D symptoms. The average values of non-missing postbaseline will be derived for the following variables:

The primary endpoint: BSFS score;

The secondary endpoints: the worst abdominal pain score, the worst abdominal bloating score, the number of bowel movements and the number of urgent bowel movements.

Only non-missing postbaseline values will be used to calculate the average values. Imputation will not be applied to missing records. The denominator should be adjusted accordingly when average values are calculated.

The IBS-QOL is composed of 34 items scored on a 1-5 scale, where lower item scores indicate greater quality of life. All items are reversed prior to derivation of composite scores; thus, higher IBS-QOL total scores indicate greater quality of life. The transformation formula used for the IBS-QOL total score is

$$\text{Score} = 100 \times \frac{\text{sum of all items} - \text{lowest possible derived score}}{\text{possible sum range}}$$

Items	Lowest/Highest Possible Derived Score	Possible Sum Range
IBS-QOL total score	All items 34, 170	136

If 7 or more items are missing, the total score will be set to missing; otherwise, the total score will be calculated using the mean score of the non-missing items to replace the missing item.

All items reversed prior to derivation of overall and subscale scores: reversed score = 6 – original score.

16.3 REPEATED OR UNSCHEDULED ASSESSMENTS OF SAFETY PARAMETERS

If a participant has repeated assessments before the start of the first treatment, the results from the final non-missing assessment made prior to the start of the study treatment will be used as baseline. If end-of-treatment assessments are repeated or if unscheduled visits occur, the last non-missing postbaseline assessment will be used as the end-of-treatment assessment for generating summary statistics. However, all postbaseline assessments will be used for PCS value determinations, and all assessments will be presented in the data listings.

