Infrequent, medically important risks reported with eluxadoline in clinical studies were (1) mild transient pancreatitis or rapidly reversible elevation of transaminases associated with abdominal pain, both consistent with sphincter of Oddi (SO) spasm or biliary sludge, and (2) pancreatitis associated with heavy alcohol consumption. Some of these events led to brief hospitalizations, but all had favorable outcomes with no sequelae. There were 13 cases that were adjudicated as SO spasm with an overall occurrence rate of 0.58%. Cholecystectomy status was known in 12 of the 13 patients, and all 12 patients where status was known had no gall bladder. In the postmarketing setting, severe cases of acute pancreatitis, sometimes fatal, were observed following the use of eluxadoline in patients without a gallbladder. Because of this, use of eluxadoline in patients without a gallbladder is contraindicated.

More detailed information about the known and expected benefits and risks and reasonably expected AEs of eluxadoline may be found in the Investigator's Brochure (IB) and/or package insert.

4. Objectives and Endpoints

Objectives	Endpoints
Primary	

 To evaluate the efficacy of eluxadoline 100 mg BID in IBS-D participants with evidence of BAM compared to IBS-D participants without evidence of BAM To evaluate the safety and tolerability of eluxadoline 100 mg BID in IBS-D participants with evidence of BAM and in IBS-D participants without evidence of BAM 	
 Change from baseline in average BSFS score over 4 weeks of treatment period Evaluation of adverse events, clinical laboratory tests, vital signs, physical examinations
Secondary	

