9.4.3. Clinical Safety Laboratory Assessments

- See Appendix 2, Section 12.2 for the list of clinical laboratory tests to be performed and the SoA for the timing and frequency.
- The investigator must review the laboratory report, document this review, and record any clinically relevant changes occurring during the study in the AE section of the CRF. The laboratory reports must be filed with the source documents. Clinically significant abnormal laboratory findings are those which are not associated with the underlying disease, unless judged by the investigator to be more severe than expected for the participant's condition.
- All laboratory tests with values considered clinically significantly abnormal during participation in the study or within 2 weeks after the last dose of study treatment should be repeated until the values return to normal or baseline or are no longer considered clinically significant by the investigator or medical monitor.
 - If such values do not return to normal/baseline within a period of time judged reasonable by the investigator, the etiology should be identified and the sponsor notified.
 - All protocol-required laboratory assessments, as defined in Appendix 2, Section 12.2, must be conducted in accordance with the SoA.
 - If laboratory values from non-protocol specified laboratory assessments performed at the institution's local laboratory require a change in participant management or are considered clinically significant by the investigator (eg, SAE or AE or dose modification), then the results must be recorded in the eCRF.

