11.2 CLINICAL LABORATORY PARAMETERS

Descriptive statistics for clinical laboratory values (in SI units) at baseline, at end-of-treatment, changes from the baseline to end-of-treatment will be presented by participant group for the following laboratory parameters:

[figure not shown]

Table 11.2–1. Criteria for Potentially Clinically Significant Laboratory Tests

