16.0 DATA HANDLING CONVENTIONS

16.1 VISIT TIME WINDOWS

Table 16.1–1 presents the visits assigned for efficacy and safety analyses and the corresponding range of treatment days (window) during which an actual visit may occur.

Table 16.1–1. Visit Time Windows

Derived Visit	Scheduled Visit Day^a	Window
Visit 1 (Screening)		
Visit 2 (Pre-treatment)		
Visit 3 (Baseline)	Day 1	Days \leq 1
Visit 4	Day 15	Days [2, 21]
Visit 5 (End of Treatment ^b)	Day 29	Days \geq 22 and last dose day +1
Visit 6	Day 33	Days \geq last dose day + 2

a Relative to the date of the first dose of treatment period. Day 1 = the date of the first dose of study treatment. There is no Day 0.
b Presented in analysis tables for safety parameters, including but not limited to clinical laboratory values and vital signs.

If the assessment date (if the assessment date is unavailable, use visit date instead) is on or after the date of the first dose of study treatment, the study day is calculated by assessment date – date of the first dose of study treatment + 1. If the assessment date is before the date of the first dose of study treatment, the study day is calculated by assessment date – date of the first dose of study treatment. Therefore, a negative day indicates a day before the start of the study treatment.

If a participant has 2 or more visits within the same window, the last visit with a non-missing value will be used for analysis.

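### SAP 16.3 puts no time limit on the end-of-treatment value, contradicts Table 16.1-1, and can pull the end-of-treatment laboratory summaries toward recovered values

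*SAP*

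**What the plan says.** SAP 16.3 governs safety parameters. Its replacement rule has two triggers: a repeated end-of-treatment assessment, or an unscheduled visit. In either case "the last non-missing postbaseline assessment will be used as the end-of-treatment assessment for generating summary statistics". The next sentence limits the reach of the rule: "all postbaseline assessments will be used for PCS value determinations, and all assessments will be presented in the data listings".

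Table 16.1-1 in SAP 16.1 gives the Visit 5 (End of Treatment) window as "Days \geq 22 and last dose day +1". That wording is loose, but Visit 6 starts at last dose day + 2, so Visit 5 must end the day before. A footnote says Visit 5 is what the safety tables present, and names laboratory values and vital signs. If two visits fall in one window, the last non-missing one is used.

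SAP 11.2 summarises laboratory values "at baseline, at end-of-treatment, changes from the baseline to end-of-treatment will be presented by participant group". SAP 11.3 does the same for vital signs.

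Protocol 9.4.3 applies to laboratory results judged abnormal to a clinically significant degree, whether found while the participant is in the study or up to 2 weeks after dosing ends. Such tests "should be repeated until the values return to normal or baseline or are no longer considered clinically significant by the investigator or medical monitor".

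**The concern.** The protocol's repeat rule and the SAP's last-value rule interact. A clinically significant abnormal laboratory value starts a series of repeats, and the series ends when the value has recovered enough to meet one of three stopping conditions. If the last value in the series stands as the end-of-treatment value, the summary uses a number chosen because it recovered. Values that are not clinically significantly abnormal start no such series, so this replacement runs one way.

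Many of the later repeats will be off drug. Protocol 8.1 requires treatment to stop for signs of drug-induced liver injury, and Protocol 8.1.1 and 8.1.2 rule out temporary interruption and rechallenge.

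Laboratory tests belong to a primary objective (safety and tolerability). Among the infrequent, medically important risks, Protocol 3.3 names "rapidly reversible elevation of transaminases associated with abdominal pain", which is the pattern a last-value rule blunts. There is also a plain programming problem: from the same SAP, two programmers could produce different end-of-treatment tables.

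**Working it through.** The plan gives no figure to reproduce on this point. The check sets the rules side by side and then does simple arithmetic on assumed values.

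**1. The two rules on the same samples.** Assume the last dose is on Day 28 (4 weeks × 7 days).

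| Sample | Days after last dose | SAP 16.1 | SAP 16.3, read literally |
|---|---|---|---|
| Visit 5, Day 29 | 1 | Visit 5 | End of treatment only if it is the last non-missing value |
| Repeat, Day 30 | 2 | Visit 6 | End of treatment if last |
| Repeat, Day 42 | 14 | Visit 6 | End of treatment if last |

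From last dose day + 2 onward the two sections disagree. Protocol 9.4.3 covers abnormal values found up to 14 days after the last dose and puts no end date on the repeats themselves, so the disagreement can extend past Day 42.

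**2. Which summaries are exposed.**
- Exposed: the laboratory mean, SD, median, minimum, maximum and change from baseline at end of treatment (SAP 11.2).
- Not exposed: PCS determinations and listings, because SAP 16.3 keeps every value for them, and adverse event records, because Protocol 9.4.3 has clinically relevant changes recorded there. Protocol 10.3.3 lists potential Hy's law and liver-injury cases as separate summaries, and no visible text ties them to the end-of-treatment value.
- Vital signs: Protocol 9.4.2 calls for one reading each and has no rule to repeat until resolution. Only the unscheduled-visit clause applies.

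**3. Size, by illustration.** Inputs: n = 12 per cohort (SAP 14.0). Assume that k participants have a rise r above baseline at Visit 5 that recovers fully on repeat, and that all others have zero change.

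Mean change using the Visit 5 value = k × r / 12. Mean change using the last repeat = 0.

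| k | r (× ULN, assumed) | Mean change, Visit 5 value | Maximum change, Visit 5 value | Mean and maximum, last repeat | PCS count if the rise meets the criterion, either rule |
|---|---|---|---|---|---|
| 1 | 2 | 2/12 = 0.17 | 2 | 0 and 0 | 1/12 (8.3%) |
| 1 | 4 | 4/12 = 0.33 | 4 | 0 and 0 | 1/12 (8.3%) |
| 1 | 9 | 9/12 = 0.75 | 9 | 0 and 0 | 1/12 (8.3%) |
| 2 | 4 | 8/12 = 0.67 | 4 | 0 and 0 | 2/12 (16.7%) |
| 2 | 9 | 18/12 = 1.50 | 9 | 0 and 0 | 2/12 (16.7%) |

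In this set-up the mean, SD and maximum move, while the median and minimum stay at 0. Partial recovery to a residual s gives a smaller shift, k × (r − s)/12.

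**4. Would Table 16.1-1 alone be enough?** Not quite.
- Protocol Table 5-1 schedules Visit 5 on Day 29 ± 2, that is Days 27 to 31. With the last dose on Day 28, a valid Visit 5 on Day 30 or 31 falls in the SAP's Visit 6 window.
- For an early stopper with a last dose on, say, Day 10, last dose day + 1 is Day 11. Visit 5 opens at Day 22, so the window is empty. An early-termination sample on Day 12 meets both the Visit 4 window (Days 2 to 21) and the Visit 6 window (from last dose day + 2).

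**The case against.** The strongest reply is that SAP 16.3 should be read with 16.1. On that reading it only breaks ties among repeats inside the Visit 5 window, which matches the last-in-window rule in 16.1 and the footnote naming Visit 5 as the visit presented. A repeat two weeks off drug would then belong to Visit 6 and replace nothing. This reading is possible, but 16.3 neither refers to the window nor limits unscheduled values to it. Even inside the window, choosing the last repeat still favours recovery.

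A second reply is that the event may be rare. Protocol 3.3 reports 13 adjudicated sphincter of Oddi spasm cases, a rate of 0.58%. All 12 with known status had no gallbladder, and such patients are excluded here (exclusion 1.02). Even at 0.58%, the chance of at least one case is 1 − 0.9942^24 ≈ 13% among 24 participants and 1 − 0.9942^12 ≈ 7% in a cohort of 12. That is fair for this event, which must also be reported to the sponsor within 24 hours. It does not cover every laboratory abnormality that could trigger repeats, and the contradiction between the two sections exists whether or not an event occurs.

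A reader might infer that the plan erases on-drug liver abnormalities. The documents do not support that: PCS determinations, listings, adverse event records and the Hy's law and liver-injury summaries retain them. A reader might also infer that every replaced value is an off-drug value. Repeats taken during treatment or by last dose day + 1 are not clearly off drug.

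**Conclusion.** The point holds for the continuous end-of-treatment summaries. SAP 16.3 and Table 16.1-1 contradict each other on late values. Followed literally, 16.3 combined with Protocol 9.4.3 can bias the laboratory mean, spread, extremes and change toward normal. The end-of-treatment table could then show no rise where the PCS table shows one.

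The size cannot be known from the documents. The shift of r/12 per participant assumes full recovery, zero change in the other 11, and a repeat series that ends after Visit 5. It does not carry over to vital signs as a recovery effect.

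One limit on the check: the schedule of activities and most of SAP 11.2, including the laboratory PCS criteria, are not visible, so the scheduled laboratory times could not be confirmed.

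**What to change.** In SAP 16.3:
- Define the end-of-treatment value as the scheduled Visit 5 assessment within its protocol visit window or, for participants who stop early, the early-termination assessment.
- Delete the unscheduled-visit clause from the replacement rule.
- Report later repeats and unscheduled values as post-treatment follow-up, and use them for PCS determinations and listings only.

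In SAP 16.1 and 16.3 together:
- State one within-window tie-break, the same in both sections and not driven by recovery. One option is to use the scheduled sample unless it was invalid, which also lets a corrective repeat replace a faulty sample.
- Reword the Visit 5 row of Table 16.1-1 so that it covers early stoppers before Day 22 and does not push a valid Visit 5 on Day 30 or 31 into Visit 6.

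The cost is a short SAP edit and a programming rule, with no new data. The end-of-treatment summary may look slightly less favourable. An early-termination sample may still be taken after the drug was stopped, so the tables should say so.

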16.4 MISSING DATE OF THE LAST DOSE OF STUDY TREATMENT

When the date of the last dose of study treatment is missing for a participant in the Safety Population, all efforts should be made to obtain the date from the Investigator. If after all efforts are made it is still missing, the last available dosing record date will be used as the last dose date.

16.5 MISSING SEVERITY ASSESSMENT FOR ADVERSE EVENTS

If severity is missing for an AE that started before the date of the first dose of study treatment, an intensity of mild will be assigned. If severity is missing for an AE that started on or after the date of the first dose of study treatment, an intensity of severe will be assigned. The imputed values for severity assessment will be used for the incidence summary; the values will be shown as missing in the data listings.

16.6 MISSING CAUSAL RELATIONSHIP TO STUDY DRUG FOR ADVERSE EVENTS

If the causal relationship to the study treatment is missing for an AE that started on or after the date of the first dose of study treatment, a causality of yes will be assigned. The imputed values for causal relationship to study treatment will be used for the incidence summary; the values will be shown as missing in the data listings.

[figure not shown]
16.7 MISSING DATE INFORMATION FOR ADVERSE EVENTS

[figure not shown]

[figure not shown]
[figure not shown]

[figure not shown]
16.8

**MISSING DATE INFORMATION FOR PRIOR OR
CONCOMITANT MEDICATIONS**

17.0

CHANGES TO ANALYSES SPECIFIED IN PROTOCOL

There are no changes to the analyses specified in the latest protocol (dated 19 Oct 2017).

18.0

REFERENCES

N/A
